8.3 Secondary objectives and outcome measures

Objective	Outcome measure	Time point(s) of evaluation of this outcome measure (if applicable)
1. To compare the effect on HRQoL of both treatment arms	HRQoL using standard, validated patient-reported outcome measures (PROMs) questionnaires: IPSS, EQ-5D-5L, EPIC and MAX- PC (Modified 18 item)	Baseline, 6wks post- treatment and 3mths, 6mths, 12mths post-randomisation, thereafter every 12 months until the end of the study.
2.To compare the effect on health care resource	Health care resource utilisation and cost-effectiveness in terms	Baseline, 3mths, 6mths, 12mths post-randomisation,

		· · · · · · · · · · · · · · · · · · ·
utilisation of both treatment arms	of cost per quality-adjusted life year (QALY)	thereafter every 12 months until the end of the study.
3.To compare the short and medium term serious adverse events related to treatments in both treatment arms	Short, medium and long-term serious adverse events related to treatments	Short term: 31 days Medium term: 3 years
4.To determine the proportion of patients needing repeat partial ablation treatment	Proportion of patients needing repeat PA treatment in the PA group	Documentation of the need for repeat PA treatment in the PA group – at 1 year post- treatment and 3 years post- treatment (for those that reach this time point in the study's lifetime)
5.To evaluate the accuracy of current mpMRI imaging and biopsy protocols in determining suitability of patients for PA	The proportion of prostatectomy patients who develop high-risk disease or bilateral intermediate disease	After histopathological evaluation (only in men who have had RP, including salvage RP)
6.To determine disease progression beyond the prostate, including local spread and development of metastases	Time to disease progression (including local and distal recurrence)	At a minimum 12 months post-randomisation follow-up of the last recruited participant, but will be longer for those recruited early in the study.
7.To determine medium-term disease-specific and overall mortality	Time to disease-specific and overall mortality	At a minimum 12 months post-randomisation follow-up of the last recruited participant, but will be longer for those recruited early in the study.

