8.5 Definition of primary treatment failure

Primary treatment failure will be determined by repeat prostate biopsies (either as part of the routine protocol-defined time point), or "for cause", or clinical appearance of symptoms demonstrating disease progression, or radiological concerns on repeat imaging, or due to clinical concern. Primary treatment failure is defined according to the treatment received:

Treatment Arm	Treatment received within arm	Definition of primary treatment failure	
Partial Ablation	HIFU or IRE	 Any of the following: a) persistent intermediate-risk PCa in a treated area after one repeat PA treatment b) repeat PA treatment requiring more than 75% of the prostate to be treated, and/or indication for radical treatment c) positive biopsies demonstrating high-risk PCa (Gleason Grade Group 4-5) at any time d) extra-prostatic disease progression defined by imaging, clinical examination, or biopsy findings e) the development of systemic disease requiring long-term androgen deprivation therapy 	
Radical Treatment	Radical prostatectomy (RP)	 Any of the following: a) a rising serum PSA reaching ≥0.2 ng/ml following initial reduction to <0.1 ng/ml after surgery b) a failure of serum PSA to fall below 0.1 ng/ml after surgery c) clinical progression to local recurrence/systemic disease d) the need for long-term androgen deprivation therapy 	
	Radical radiotherapy (RRT) or low dose- rate brachytherapy (LDR-B)	 Defined using the RTOG-ASTRO Phoenix criteria (48) as: a) a rise of post-treatment PSA ≥2.0 ng/ml above the post-treatment nadir or b) clinical progression to systemic disease with the need for long-term androgen deprivation therapy 	

Further information regarding diagnosis and management of primary treatment failure can be found in section 16.4.

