11.4 Exclusion Criteria for entry into the main study

A patient with not be eligible for the study if **ANY** of the following apply:

1. Taking part in another therapeutic PCa clinical trial or has been involved in such trials within the previous 4 months (N.B. the TRANSLATE trial is a diagnostic trial and co-enrolment is permitted)

- 2. PSA > 20 ng/ml within the last 120 days
- 3. Unfit for radical treatment or general anaesthesia or cannot tolerate transrectal ultrasound
- 4. In the opinion of the treating physician, has a contraindication to either HIFU or IRE
- 5. Not suitable for mpMRI or have a single or bilateral hip replacement
- 6. Has evidence of extraprostatic extension by mpMRI, or clinical or radiological ≥T3 disease
- 7. Concomitant cancer or previous active treatment for PCa
- 8. Evidence of metastatic disease
- 9. Bilateral intermediate risk disease or higher
- 10. Low-risk (Gleason Grade Group 1) disease only, or high-risk (Grade Group ≥4) PCa only
- 11. History of acute urinary retention within the last 6 months prior to entry to the study
- 12. Prostatic calcification and cysts causing ultrasonic shadowing or greater than 1cm (for HIFU)
- 13. History (within 3 years) of inflammatory bowel disease or any condition that may increase the risk of recto-urethral fistula formation (for HIFU)
- 14. Has known hypersensitivity to pancuronium bromide, atracurium or cistracurium, or any medical condition such that muscle relaxation cannot be administered as part of a general anaesthetic
- 15. Has a history of bladder neck contracture
- 16. Had active treatment for a malignancy within 3 years, including malignant melanoma, except other types of skin cancer
- 17. Has any active implanted electronic device (e.g., pacemaker)
- 18. Is unable or unwilling to be catheterised
- 19. Has had prior or current PCa therapies
- 20. Has had prior transurethral prostatectomy (TURP), stricture surgery, urethral stent or prostatic implants
- 21. Has had prior major rectal surgery (except haemorrhoids)
- 22. Is actively bleeding, is anticoagulated or on blood thinning medications that cannot be stopped for the peri-operative period for a PA procedure, or has a significant bleeding disorder that may affect the peri-operative period as judged by the clinical staff.
- 23. Unable to give consent to participate in the study as judged by the clinical staff
- 24. Wishing to maintain future fertility

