13.2.2 Radical Prostatectomy (RP)

Patients randomised to the radical treatment group for whom the preferred treatment option is surgery will undergo open, laparoscopic or robot-assisted RP according to local centre expertise, patient preference and clinical judgement. Centres included in PART all have cancer network recognised MDTs and cancer centre status. Robot-assisted laparoscopic surgery is recommended, but centres that perform open RP can also participate; this reflects current practice in that a small number of NHS centres continue to perform open surgery, and for clinical reasons some patients may require open surgery. Recent cohort studies confirm similar side effect profiles from both procedures ((35,36)). Routine histopathology evaluation of the surgical resection specimens will be performed by local pathology departments. As per NHS standard care, if disease progression is suspected as per the definition of a post-RP PSA rising to ≥ 0.2 ng/ml then the patient will be re-staged with imaging. Patients will be fully informed about their disease grade, clinical stage and the various treatment options, risks and possible outcomes.

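### Secondary outcome 5 tests selection for partial ablation against prostatectomy pathology but does not count extraprostatic disease that the work-up missed

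*Protocol*

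**What the plan says.** Protocol section 8.3, objective 5, sets out to "evaluate the accuracy of current mpMRI imaging and biopsy protocols in determining suitability of patients for PA". The outcome measure is "The proportion of prostatectomy patients who develop high-risk disease or bilateral intermediate disease", and its time point is "After histopathological evaluation (only in men who have had RP, including salvage RP"). Whole-gland pathology is therefore the reference against which the pre-treatment work-up is judged.

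Section 11.4 restricts entry on disease extent in three ways:
- stage, exclusion 6: "Has evidence of extraprostatic extension by mpMRI, or clinical or radiological ≥T3 disease"
- laterality, exclusion 9: "Bilateral intermediate risk disease or higher"
- grade, exclusion 10: "Low-risk (Gleason Grade Group 1) disease only, or high-risk (Grade Group ≥4) PCa only"

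Inclusion 4 in section 11.3 also sets a clinical stage ceiling of T2b.

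Section 8.5 uses *high-risk* in the PA failure definition, item (c): "positive biopsies demonstrating high-risk PCa (Gleason Grade Group 4-5) at any time". Extra-prostatic progression is a separate item, (d). Section 13.2.2 states: "Routine histopathology evaluation of the surgical resection specimens will be performed by local pathology departments".

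**The concern.** An accuracy outcome should count the errors that the work-up can make. For PA selection the protocol screens on grade, laterality and stage, and the outcome looks for error in the first two only. The missing one is the criterion in which mpMRI is named as the test.

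At stake is how the trial's figure on its own selection pathway will be read. Section 7.4 treats accurate imaging and mapping of the disease as essential to a PA strategy. A proportion that leaves out undetected extraprostatic disease will look more favourable than one that includes it, and a reader of the results could not tell by how much.

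**Working it through.** The plan gives no figure for this outcome, so there is none to reproduce. The check is a comparison of definitions, followed by an illustration.

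**Step 1. Match the outcome to the entry criteria on disease extent.**

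| Feature | Entry criterion | In outcome 5? |
|---|---|---|
| Grade Group ≥4 | Exclusion 10 | Yes, as high-risk disease |
| Bilateral intermediate-risk disease | Exclusion 9 | Yes |
| Extraprostatic extension or ≥T3 | Exclusion 6; inclusion 4 (≤T2b) | No |

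**Step 2. Could stage enter through the term *high-risk*?** Section 8.3 does not define it. Exclusion 10 and section 8.5(c) both gloss it by Grade Group only, and section 8.5 places extra-prostatic disease under its own item. Read consistently with those sections, the term does not cover stage.

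**Step 3. Apply the definition to typical specimens.**
- Unilateral Grade Group 4: in the numerator.
- Unilateral Grade Group 2 with extension not seen on mpMRI: denominator only.
- Unilateral Grade Group 3 with seminal vesicle invasion: denominator only.

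**Step 4. Direction.** Let b be the proportion counted now and m the share of prostatectomy men with extension but neither high-grade nor bilateral intermediate disease. With extension included, the proportion is b + m. Since m ≥ 0, the present definition leaves the figure unchanged or understates it. The gap is zero only if every man with extension is already counted for grade or laterality.

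**Step 5. Illustrative size.** The documents give neither b nor the frequency of extension e. Assume b = 15%, e from 5% to 30%, and independence. Then m = (1 − b) × e, and the proportion with any of the three features is 1 − (1 − b)(1 − e).

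| e | m = 0.85 × e | Any of the three features | Reported now |
|---|---|---|---|
| 5% | 4.25% | 19.25% | 15% |
| 10% | 8.5% | 23.5% | 15% |
| 20% | 17.0% | 32.0% | 15% |
| 30% | 25.5% | 40.5% | 15% |

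With b = 10%, m runs from 0.90 × 5% = 4.5 to 0.90 × 30% = 27 points. With b = 25%, it runs from 0.75 × 5% = 3.75 to 0.75 × 30% = 22.5 points.

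**Step 6. Without independence.** If extension overlaps with the counted features as far as possible, m falls to max(0, e − b). For b = 15% that is 0 at e = 5% or 10%, 5 points at e = 20%, and 15 points at e = 30%.

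**The case against.** The strongest case against the point has five parts.

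*Exclusion 6 is a pre-treatment criterion.* A reader might infer that these men are unsuitable under exclusion 6, or were wrongly enrolled. The documents do not support that. The exclusion is written for mpMRI, clinical or radiological evidence, and a man whose extension appears only under the microscope did not breach it. This limits the wording but does not remove the point: he has the condition the criterion screens for, and the work-up missed it. The outcome already treats grade this way, since a Grade Group 4 specimen counts although biopsy did not show it.

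*The outcome defines no category of correct staging.* A reader might say that such men are scored as correctly staged. The protocol does not say so. It asks only for a proportion with listed features, and these men are absent from the numerator.

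***High-risk* is undefined in section 8.3.** The grade-only glosses sit in an entry exclusion and a biopsy-based failure criterion, and inclusion 4 links intermediate risk to a stage limit. A stage-inclusive meaning at prostatectomy cannot be ruled out. It would, however, differ from sections 8.5 and 11.4 and would have to be stated. The components are fixed in the protocol, so adding one is not a detail to leave to the SAP.

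*Other outcomes bear on extraprostatic disease.* Failure item (d) in section 8.5 and secondary objective 6 record progression beyond the prostate, including in men given PA. It would therefore be too strong to call outcome 5 the only evidence on whether selection was sound. Those outcomes measure later consequences, though, and do not compare the work-up with whole-gland pathology.

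*The size is assumed.* This stands in full. The documents supply neither rate, and independence is a convenience.

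**Conclusion.** The point holds as a gap in the definition of one secondary outcome. Read with the protocol's own use of *high-risk*, outcome 5 does not count extraprostatic or ≥T3 disease that the work-up missed, and so can only leave unchanged or understate the proportion mis-selected.

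The understatement equals the share of prostatectomy men with extension but neither high-grade nor bilateral intermediate disease. That share cannot be derived from the documents. The range of about 4 to 26 points rests on an assumed 15% counted now, assumed extension in 5-30%, and independence. It is smaller if extension clusters with high grade, and it should not be read as an estimate of bias in this trial.

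The finding does not show that ineligible men are enrolled, and it questions no eligibility or treatment rule. It does not touch the co-primary analyses, the alpha level or the sample size.

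**What to change.** In section 8.3, outcome 5:

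1. Add pathological extraprostatic extension/≥pT3 as a third component.
2. Report each component separately as well as the composite, so that the present two-component figure remains available.
3. State that *high-risk* means Grade Group ≥4, as in sections 8.5 and 11.4. If a stage-inclusive meaning was intended, say so and reconcile it with those sections.
4. Replace *develop* with *are found to have*, since the specimen shows disease present at surgery.
5. Ensure that pathological stage is captured on the CRF from the routine histopathology report. The data lists in section 16.6 do not name prostatectomy pathology, and the CRF itself is not shown, so the field may already exist.

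The cost is a wording change, at most one extra data field, and a reported figure that may be less favourable. No new test is needed, because the specimens are already examined routinely.

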16.4 Additional treatment/treatment failure

Partial Ablation Arm

Where a positive biopsy result is returned for intermediate-risk PCa during the study follow-up period, either in the previously treated area or in a previously untreated area (demonstrating new intermediate-risk disease), participants will be offered ONE repeat PA treatment of the positive biopsy area.

Primary treatment failure following PA will be determined by repeat prostate biopsies – per protocol or "for cause" or clinical appearance of symptoms/signs/imaging demonstrating disease progression, or due to clinical concern. Biopsies will result in one of four pre-defined scenarios:

- Scenario 1: Negative biopsies, in which case the patient will continue to be followed-up as described.
- Scenario 2: Positive biopsies in a previously untreated or treated area of the prostate demonstrating low-risk low-volume disease, in which case the patient will not require additional treatment and follow-up will continue.
- **Scenario 3:** Positive biopsy for intermediate-risk PCa in the previously treated area, in which case the patient will be offered one repeat PA treatment of the positive biopsy area.
- **Scenario 4:** Positive biopsy for intermediate-risk PCa in a previously untreated area, demonstrating new intermediate-risk disease, in which case the patient will be offered one repeat PA treatment.

Refer to the flow chart below.

Radical treatment arm

For participants in the radical treatment arm receiving RP additional treatment, options will be discussed with the participant, as per standard NHS care. This is usually salvage radiotherapy post-RP with or without androgen deprivation therapy, or androgen deprivation alone. Salvage RP or androgen deprivation will usually be offered where appropriate if post-RRT or LDR-B treatment failure occurs, as per NHS standard care. Refer to flow charts below.

Management of primary treatment failure

Where treatment failure is diagnosed, the patient will be re-staged as appropriate with cross-sectional imaging, and additional appropriate treatment options will be discussed with the participant, as per standard NHS care. For participants in the PA arm these may include salvage RP, external beam RT, or long-term androgen-targeted therapy +/- chemotherapy. For patients in the radical therapy arm this may include an appropriate salvage therapy, or long-term androgen-targeted therapy +/- chemotherapy.

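### Secondary outcome 5 pools salvage with primary prostatectomy specimens, so the apparent error of mpMRI and biopsy staging is probably overstated and depends on how many men fail treatment

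*Protocol*

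**What the plan says.** The aim of objective 5 in Protocol section 8.3 begins "To evaluate the accuracy of current mpMRI imaging and biopsy protocols in determining" and ends with suitability for PA. Its only outcome measure is "The proportion of prostatectomy patients who develop high-risk disease or bilateral intermediate disease". The third column of the same row gives timing and source: "After histopathological evaluation (only in men who have had RP, including salvage RP").

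Section 16.4 describes two routes to salvage RP, both after failure:
- PA arm, once treatment failure is diagnosed: "For participants in the PA arm these may include salvage RP, external beam RT, or long-term androgen-targeted therapy +/- chemotherapy".
- Radical arm, after radiotherapy or brachytherapy: "Salvage RP or androgen deprivation will usually be offered where appropriate if post-RRT or LDR-B treatment failure occurs".

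Section 8.5 lists among the PA failure criteria "positive biopsies demonstrating high-risk PCa (Gleason Grade Group 4-5) at any time". It also counts an indication for radical treatment as a PA failure.

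At entry, section 11.4 excludes "Bilateral intermediate risk disease or higher" and disease that is only high-risk. The outcome therefore counts findings that the entry work-up was meant to rule out. The protocol does not separate primary from salvage specimens and sets no limit on the interval between the work-up and the specimen.

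**The concern.** A prostatectomy specimen can show what imaging and biopsy missed if the gland is untreated and the man was not chosen for surgery because of a bad outcome. Primary RP broadly meets both conditions. Salvage RP meets neither, because the gland has been ablated or irradiated and the man is there because treatment failed. Men whose PA, radiotherapy or brachytherapy succeeds supply no specimen.

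A single pooled proportion therefore mixes disease missed at the work-up with disease that appeared or progressed later. The verb in the outcome measure, *develop*, invites that mixing. The estimate would then move with the failure rate, the uptake of salvage surgery and the length of surveillance, none of which is a property of mpMRI or biopsy. A reader using it to judge whether current staging selects men well enough for PA could be misled.

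**Working it through.** **Does the text select salvage specimens on failure?** Yes.

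1. Section 16.4 offers salvage RP after PA failure, or after radiotherapy or brachytherapy failure. It gives no other route.
2. Section 8.5 makes Grade Group 4-5 on biopsy a PA failure at any time. High-risk disease is thus both a route to salvage RP and one of the two findings the outcome counts.
3. Sections 13.1.4 and 16.4 (Scenario 4) recognise new intermediate-risk disease on the opposite side or in an untreated area after PA. If such a man later has salvage RP, that disease can contribute to a finding scored against staging, although the protocol itself calls it new.
4. PA-arm biopsies are due at 12 and 36 months (section 16.3.1), and 36-month follow-up of all participants depends on further funding (section 9.2). The number of salvage specimens varies with this; staging accuracy does not.

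**How large could the effect be?** The protocol gives no expected value or precision for this outcome, so there is no stated figure to reproduce.

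Inputs from the protocol: 400 men per arm (section 9); 10% dropout and, as the design example, 20% PA failure (section 19.2).
- Expected PA failures = 0.20 × (400 × 0.90) = 0.20 × 360 = 72.

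Inputs that are assumptions only:
- Salvage RP uptake of 10%, 25% or 50% of the 72, giving about 7, 18 or 36 salvage specimens.
- Primary RPs: 100, 160 or 240.
- Adverse pathology: 10% or 20% in primary specimens, 40% or 60% in salvage specimens.

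Formulas, with n the number of specimens and p the adverse proportion:
- pooled = (n_primary × p_primary + n_salvage × p_salvage) / (n_primary + n_salvage)
- bias = [n_salvage / (n_primary + n_salvage)] × (p_salvage − p_primary)

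| Primary RPs | Salvage RPs | Salvage share | 10% and 40% | 10% and 60% | 20% and 40% | 20% and 60% |
|---|---|---|---|---|---|---|
| 240 | 7 | 2.8% | 10.9% | 11.4% | 20.6% | 21.1% |
| 160 | 18 | 10.1% | 13.0% | 15.1% | 22.0% | 24.0% |
| 100 | 36 | 26.5% | 17.9% | 23.2% | 25.3% | 30.6% |

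Column heads give p_primary and p_salvage; cells give the pooled proportion. The largest shift is (36/136) × (0.60 − 0.10) = +13.2 points. The smallest shown is (7/247) × (0.40 − 0.20) = +0.6 points.

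A second low case, with 200 primary RPs at 25% and 7 salvage RPs at 50%, gives (50 + 3.5)/207 = 25.8%, a bias of +0.8 points.

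**Can it go the other way?** The bias is zero if the two proportions are equal. With p_primary 20% and p_salvage 10% it runs from −0.3 points (240 and 7) to −2.6 points (100 and 36).

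Salvage RPs after radiotherapy or brachytherapy failure are not counted here and would add further selected specimens.

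**The case against.** **The salvage wording sits in the time-point column, and the analysis plan could split the two groups.** Section 19.4 gives no method for objective 5, and a split table would be ordinary SAP content. That is fair, but the outcome measure names a single proportion of prostatectomy patients and section 8.3 expressly brings salvage RP into it. A SAP that follows this definition inherits the pooling.

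**The objective does not say baseline.** It refers to current imaging and biopsy protocols, and suitability for PA is judged again before a repeat ablation. Salvage RP is also the only route to whole-gland histology in men who received PA. This is a good reason to keep and report the salvage pathology. It does not justify averaging that pathology with primary specimens in one figure.

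**Primary RP is not a perfect reference.** A reader might infer that primary specimens closely follow the work-up and give an unbiased answer. The documents do not support that. The mpMRI may be up to 6 months old at entry (section 11.3), treatment may start up to 12 months after randomisation (section 6), and men reach RP by shared decision or clinician recommendation (section 13.2.1). What stands is narrower: they are not selected on failure and their glands are untreated.

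**The direction is not proven.** Persistent intermediate-risk disease in a treated area is a PA failure without being high-risk or bilateral. Failure after radiotherapy or brachytherapy is defined by PSA or systemic progression. Ablation may remove one side of bilateral disease. This stands, so an upward bias is likely but not certain.

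**Conclusion.** The point holds as a defect in the definition of a secondary outcome. Read as written, section 8.3 mixes failure-selected, previously treated glands with untreated ones and uses the result as a measure of staging accuracy. The bias is probably upward, because high-risk disease is itself a way into the salvage group and because later disease is counted as a staging error.

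A reader might go further and conclude that the proportion is certainly inflated, or by a definite amount. The protocol supports neither. It gives no number of primary or salvage RPs and no adverse-pathology rate for either group. Only the arm size, the dropout and the design failure rate are documented. Within the assumed inputs, the effect ranges from about one point or less, if salvage RPs are few, to about 13 points at the high end. It would vanish or reverse if salvage specimens were no more often adverse than primary ones.

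The outcome is descriptive, with no sample size or decision rule attached. Neither co-primary analysis is affected.

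**What to change.** In section 8.3, objective 5:
- Define the outcome on men in either arm whose first prostate cancer treatment is RP. Limiting it to the radical arm would needlessly drop PA-allocated men who go straight to RP, whose specimens are equally usable.
- Replace *develop* with *are found to have on the primary RP specimen*.
- Report salvage RP pathology separately, as a description of treatment failures, and carry the same split into the SAP.

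No new data and no change to clinical care are needed, provided the records show whether each RP was the first treatment. The costs are a smaller denominator and the loss of PA-treated men's whole-gland histology from the accuracy estimate, although that histology is still reported.
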